6.9 Treatment Phase Visits and Contacts

All follow-up will be based on 28-day Cycles. Post-insertion study evaluations will occur at Treatment Phase Visit 6 (Day 28 to Day 42) and Visit 7 (Day 85 to Day 105).

6.9.1 Visit 6

- Timing: Day 28 to 42
- Procedures:
 - Review of adverse events or changes in medical history since the prior visit
 - Review of concomitant medications
 - Inquire about change in sexual partner

- Collect and review daily diary for completeness
- Dispense additional diaries and feminine hygiene products as needed
- Physical examination and testing
 - High sensitivity urine pregnancy test (if positive, see Section 7.4)
 - Blood pressure, pulse and weight
 - Any clinically indicated physical examination
 - Clinically verify presence of IUS by palpation or direct visualization of strings (for missing strings management see Section 6.13 and Appendix G)
 - Chlamydia and gonorrhea testing for any subject following a change in sexual partner since the last study visit
 - Women with positive tests should be contacted and receive treatment as soon as possible without waiting for the next study clinic visit
- Instruct her to start collecting all used feminine hygiene products with evident blood between Day 57 and Day 84
 - Day 57 would include any products initiated prior to going to sleep the night before but removed on Day 57
 - Any products initiated the evening of Day 84 but removed the next morning would not be collected
- Schedule next appointment (Visit 7) ideally for Day 85 to Day 89, but up to Day 105 is allowed

6.9.2 Contact Day 50 to Day 56

- Remind subject to:
 - Start collecting all used feminine hygiene products with evident blood collection between Day 57 and Day 84
 - Day 57 would include any products initiated prior to going to sleep the night before but removed on Day 57
 - Any products initiated the evening of Day 84 but removed the next morning would not be collected

- Dispose of any used products from prior to Day 57 or after Day 84
- Confirm date and time for Visit 7 appointment

6.9.3 Visit 7 (Cycle 3)

- Timing:
 - Ideal: Day 85 to 89 (Cycle 3, days 1-5)
 - Allowable: up to day 105 (Cycle 3, days 1-21)
- Follow-up Procedures:
 - Review of adverse events or changes in medical history since the prior visit
 - Review of concomitant medications
 - Inquire about change in sexual partner
 - Collect and review daily diary for completeness
 - Subject completion of Treatment VAS questionnaire (Appendix E)
 - Dispense additional diaries and feminine hygiene products as needed
 - Physical examination and testing
 - High sensitivity urine pregnancy test (if positive, see Section 7.4)
 - Blood pressure, pulse and weight
 - Any clinically indicated physical examination
 - Clinically verify presence of IUS by palpation or direct visualization of strings (for missing strings management see Section 6.13 and Appendix G)
 - Chlamydia and gonorrhea testing for any subject following a change in sexual partner since the last study visit.
 - Women with positive tests should be contacted and receive treatment as soon as possible without waiting for the next study clinic visit
 - Collect all feminine hygiene products collected between Day 57 and Day 84
 - Interview subject for feminine hygiene collection compliance
 - Collect venous blood for:
 - Hemoglobin/hematocrit and ferritin
 - AH assay sample

- Instruct her to start collecting all used feminine hygiene products with evident blood between Day 141 and Day 168
 - Day 141 would include any products initiated prior to going to sleep the night before but removed on Day 141
 - Any products initiated the evening of Day 168 but removed the next morning would not be collected
- Schedule next appointment (Visit 8) ideally for Day 169 to Day 174, but up to Day 189 is allowed

6.9.4 Contact Day 133 to Day 140

- Remind subject to:
 - Start collecting all used feminine hygiene products with evident blood collection between Day 141 and Day 168
 - Day 141 would include any products initiated prior to going to sleep the night before but removed on Day 141
 - Any products initiated the evening of Day 168 but removed the next morning would not be collected
 - Dispose of any used products from prior to Day 141 or after Day 168
 - Confirm date and time for Visit 8 appointment

6.10 Study Treatment Phase Completion/Early Discontinuation (Visit 8)

- Timing:
 - Completion of 6 cycles of LNG20 IUS use
 - Ideal: Day 169 to Day 174 (within 5 days of completing 6 cycles)
 - Allowable: up to Day 189 allowed (up to 21 days after completing 6 cycles)
 - Early discontinuation
- Procedures:
 - Review of adverse events or changes in medical history since the prior visit
 - Review of concomitant medications
 - Inquire about change in sexual partner
 - Collect and review daily diary for completeness

- Subject completion of Treatment VAS questionnaire
- High sensitivity urine pregnancy test (if positive, see Section 7.4)
- Weight, pulse and blood pressure
- Any clinically indicated physical examination
- Clinically verify presence of IUS by palpation or direct visualization of strings (for missing strings management see Section 6.13 and Appendix G)
- Chlamydia and gonorrhea testing for any subject following a change in sexual partner since the last study visit.
 - Women with positive tests should be contacted and receive treatment as soon as possible
- Breast and pelvic exam (if not performed within the last 3 months)
- IUS removal
 - If participant has contraindication to continuing IUS use or desires removal then perform IUS removal procedure
 - If no indication for removal, discuss option of continuing IUS or removal; remove IUS for all women that desire to discontinue IUS
- Retain all removed or expelled IUSs as described in the Study Reference Manual
- Collection of feminine hygiene products:
 - If completed full protocol: collect all products collected between Day 141 and Day 168
 - If early discontinuation coinciding with Visit 7 (Cycle 3): collect all products collected between Day 57 and Day 84
 - If early discontinuation not coinciding with a complete Visit 7 or Visit 8 collection window: no product collection
- If collected feminine hygiene products:
 - Interview subject for feminine hygiene collection compliance
 - Collect venous blood for:
 - hemoglobin/hematocrit and ferritin (if not obtained within the prior 6 weeks)
 - AH assay sample

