6.1 Alkaline Hematin Menstrual Blood Loss Assessment

This study will utilize the AH method to assess MBL. Participants will be provided with branded study-specific feminine hygiene products to be used exclusively during study participation. During the Screening Phase all feminine hygiene products used during a menses with any evident bleeding will be collected for analysis, stored at room temperature and provided to the site. During the Treatment Phase, all feminine hygiene products used during only Cycles 3 and 6 will be collected for analysis. A daily bleeding diary will be completed indicating the highest level of bleeding experienced for each day. A venous blood sample will be obtained after each menses or cycle evaluated. The collected venous blood samples and feminine hygiene products will be shipped to KCAS, LCC laboratory for AH analysis after each Screening Phase Visits 2-4, as applicable, and Treatment Phase Visits 7 and 8. Used feminine hygiene products that are brought by the subject to the site that do not require analysis will be appropriately disposed of.

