5.3.3 Missing Data for MBL

- A MBL assessment by AH may not be collected for Treatment Phase Cycle 3 and Cycle 6 in which a subject reported being amenorrheic (no spotting/bleeding) for the 28-day collection interval on the CRF for AH Menstrual Blood Loss Assessment; in this case the corresponding MBL value will be set to 0 mL. Additionally, the participant may report spotting only or light bleeding on her diaries with no feminine hygiene products used; in this case the corresponding MBL value will be set to 0 mL
- For a Treatment Phase missed Visit 7 (Cycle 3) or missed Visit 8 (Cycle 6), no imputation of MBL from diary data alone will be conducted.
- For the evaluations of MBL, the last observation carried forward (LOCF) method will be used for imputation. If MBL data in Cycle 3 are available but no MBL data in Cycle 6 are available or Cycle 6 is invalid, then MBL data in Cycle 3 will be used as End of Study MBL.
- Additional imputation method(s) might be explored for sensitivity analysis when deemed necessary

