9.2 Primary Efficacy Variables

The primary outcome measure will be the proportion of subjects with successful treatment of heavy menstrual bleeding based on the decrease in MBL from baseline to end of treatment after initial LNG20 IUS insertion. For the MITT and PP analysis populations, end of treatment will be defined as the last post baseline MBL value (either Treatment Cycle 3 or Treatment Cycle 6) recorded for the subject.

For the ITT-based analysis population, subjects who lack both a Treatment Cycle 3 and Treatment Cycle 6 MBL result will have the baseline MBL serve as the end of treatment recorded outcome.

A subject with successful treatment will be defined as:

- the end of treatment MBL <80 mL, and
- a decrease to a value of no greater than 50% of the baseline MBL.

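### Protocol 6.10 discards blood loss saved during an unfinished Cycle 6, so a woman already past a failure limit can stay a success by LOCF in MITT and both ITT analyses

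*Protocol*

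**What the plan says.** Protocol 6.10 gives three cases for the final visit. For completers, "If completed full protocol: collect all products collected between Day 141 and Day 168". For an exit that coincides with Visit 7, the Cycle 3 products are taken. For all other exits, "If early discontinuation not coinciding with a complete Visit 7 or Visit 8 collection window: no product collection". The AH venous sample is listed only for women whose products are collected, so it lapses as well. Protocol 6.1 adds: "Used feminine hygiene products that are brought by the subject to the site that do not require analysis will be appropriately disposed of". Appendix B marks both product collection and AH blood in its column for Visit 8 or early discontinuation, and none of its footnotes limits them to complete windows.

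SAP 9.2 defines success by two conditions: "the end of treatment MBL <80 mL, and" "a decrease to a value of no greater than 50% of the baseline MBL". Under SAP 5.3.3, when Cycle 6 is missing or invalid but Cycle 3 is available, "then MBL data in Cycle 3 will be used as End of Study MBL". SAP 6 admits a woman to MITT if she has an MBL in either cycle. It carries baseline forward (BOCF) in the ITT analyses only when both are missing. Neither document makes any use of a part-cycle collection.

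**The concern.** Women are told at Visit 7, and reminded before Day 141, to save every bloodstained product through the Cycle 6 window. A woman who attends for removal inside that window has been saving products since it opened. What she has saved is a lower bound on her loss for the cycle. If the bound is already past either limit, no imputation assumption is needed to call the cycle a failure.

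The rule in 6.10 throws that information away, and LOCF then fills the gap with Cycle 3. If she left because bleeding had become heavy again, the carried-forward value points the wrong way. The error favours success, and no later analysis can recover discarded products. At stake is a small upward bias in the primary success rate that the planned MITT and ITT analyses would not show.

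**Working it through.** **Inputs.** Cycle 6 window Days 141-168, 28 of 168 treatment days (Protocol 6.10, SAP 9.1). Expected success rate 80% and early exits up to 15% (Protocol 9.1), or 15-20% (SAP 4). Efficacy criterion: lower two-sided 95% limit of at least 70%, normal approximation (SAP 5.1). About 85% success for an LNG 52 mg IUS in a cited randomized study (Protocol 7.1.1).

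**1. The plan's own figures.** L = p − 1.96 × √(p(1−p)/n).
- n = 85, p = 0.80: 0.80 − 1.96 × √(0.16/85) = 71.5%, as in Protocol 9.1.
- n = 80, p = 0.80: 0.80 − 1.96 × √(0.16/80) = 71.2%, as in SAP 4.

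**2. When a partial total settles failure.** A partial total of 80 mL or more breaks the first condition. More than 50% of baseline breaks the second, and this is the tighter limit when baseline is below 160 mL (80/0.5). With a baseline of 80 mL, anything above 40 mL is enough. A low partial total proves nothing, because the remaining days could still add to it.

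**3. How leavers are scored.**

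| Exit during | MITT (primary) | ITT | ITT without women lost or withdrawn |
|---|---|---|---|
| Cycle 6, good Cycle 3 value | success by LOCF | success by LOCF | success by LOCF (has a post-baseline MBL, so not excluded under SAP 6) |
| Cycle 3 | not in MITT | failure by BOCF | failure by BOCF, unless lost to follow-up or consent withdrawn without IUS removal |

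The per-protocol set may drop the Cycle 6 leaver, because SAP 7.2 lists a missed Cycle 6 MBL as a major deviation. That removes her; it does not count her as a failure.

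**4. How many.** With exits spread evenly (assumption), 15 × 28/168 = 2.5 and 20 × 28/168 = 3.3 per 100 women fall in the Cycle 6 window. Only those with failing partial loss and a successful Cycle 3 matter, so the count could be zero.

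**5. Effect on the criterion**, moving k women from LOCF success to failure, with an MITT of 85 (assumption):

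| Start | k | Result | Lower limit |
|---|---|---|---|
| 68/85 (80.0%) | 0 | 68/85 | 71.5% |
| | 1 | 67/85 | 70.1%, pass |
| | 2 | 66/85 | 68.8%, fail |
| | 3 | 65/85 | 67.5%, fail |
| 72/85 (84.7%) | 0 | 72/85 | 77.1% |
| | 5 | 67/85 | 70.1%, pass |
| | 6 | 66/85 | 68.8%, fail |

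MITT includes women carried forward from Cycle 3, so it may exceed the 85 planned completers. Starting again from 80%, the count stays at two: for n = 90, 71/90 gives 70.5% and 70/90 gives 69.2%; for n = 95, 75/95 gives 70.7% and 74/95 gives 69.6%.

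**The case against.** The complete-window rule has a sound purpose: a truncated total read as a full-cycle MBL would create false successes. That stands, and any change must preserve it.

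The relevant women are few. Planned exits include dropouts, expulsions and pregnancies as well as bleeding. Protocol 7.1.1 cites 6% stopping for bleeding complaints in pooled trials, with the follow-up for that figure not stated. If all of it fell evenly within 168 days (assumption), 6 × 28/168 = 1 per 100 would leave inside the Cycle 6 window, and removal for irregular or prolonged bleeding need not mean high volume. One woman does not reverse 68/85. This stands as a limit on the size.

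Expulsion exits would gain little, because SAP 9.1 invalidates a collection when the IUS is found absent at the post-collection visit. If discontinuers were simply scored as failures, the assay would not be needed; the SAP does not do that.

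Three stronger readings are tempting, and the documents do not support them:
- That women leaving in Cycle 3 escape every analysis. They are outside MITT, but ITT with BOCF already fails them, including those who had the IUS removed.
- That one woman reverses the result. This holds only from 67/85, the minimum pass; the plan expects 68/85.
- That the 5-7 exits per 100 expected across both windows (15 to 20 × 56/168) are hidden failures. That figure counts all exits, whatever their blood loss.

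**Conclusion.** The point holds for women who leave during Days 141-168 with a successful Cycle 3 value. They stay successes by LOCF in MITT and both ITT analyses even if their saved products already prove Cycle 6 failure. Separately, 6.10 and Appendix B disagree on collection at early discontinuation and must be reconciled.

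The effect is small and its size unknown. Even timing of exits gives about 2.5-3.3 such exits per 100, only some with failing loss. At the planned 80% rate two hidden failures reverse the conclusion; at 72/85 it takes six. These counts use the SAP criterion, which rests on the lower limit alone and takes precedence over the protocol. The protocol synopsis also asks for a point estimate of at least 80%, and under that wording one reclassified woman (67/85, 78.8%) would already miss it.

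**What to change.** - **Protocol 6.10 and Appendix B.** At an early-discontinuation visit inside Days 141-168, collect and assay the products saved so far and take the AH venous sample. Make the two places agree.
- **SAP 5.3.3.** Score a partial Cycle 6 total of at least 80 mL, or above 50% of baseline, as not a success in place of LOCF. Treat any lower partial total as missing: it counts neither as an MBL assessment for MITT entry nor as the last post-baseline value, and the existing rules then apply.
- **SAP 9.1.** State that collections invalid under that section (IUS found absent, analysed beyond 56 days, laboratory failure) stay invalid when partial.
- **Partial Cycle 3 collections.** If assayed, report them as supportive only. Letting them into MITT would add women only when they fail, which makes entry depend on outcome.

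The change touches data collection and scoring only. It costs a short amendment, an AH assay for a few women who are already at a visit, and possibly a slightly lower success rate.

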6.11 Safety Follow-Up

All subjects for whom the IUS was removed will be contacted 7 to 10 days after the study exit visit to assess for any post-IUS removal bleeding and cramping (if applicable), and any IUS-related or IUS procedure-related adverse events. After completion of the Treatment Phase, all subjects with ongoing IUS-related adverse events that are not resolved or stabilized will have monthly contacts or visits, as appropriate, until the event is resolved or stabilized.

6.12 Unscheduled Visits

Subjects may require an evaluation at times other than the scheduled visits. An unscheduled visit should only be conducted when the subject reports problems that are related to the IUS, study safety issues or if repeat laboratory testing is required. In such circumstances, the unscheduled visit should be performed by a study clinician to review any change in medical history and perform any examination and testing as clinically indicated.

6.13 Diagnostic Ultrasound Examinations

Diagnostic ultrasound examinations may be required during the study for pregnancy (see Appendix F), missing IUS strings (see Appendix G), confirmation of IUS location or possible IUS related adverse events. Any time an ultrasound examination is performed for diagnostic purposes, the image must be documented in a photo or digital image to be included in the source documentation. If the exam is not documented in a formal report, a high resolution copy of the image documentation should be forwarded within 5 business days for a verifying review by the Sponsor as described in the Study Reference Manual. All ultrasound findings should be documented as follows:

- Printed image(s) with the subject's study number on the image
- Indication, impression and plan related to the images written in the source documentation

All ultrasound examination documentation should be maintained with the subject's study source documentation.

For details regarding the sponsor review of study-related ultrasound exams see the Study Reference Manual.

6.14 Pap Testing

Screening Pap testing must demonstrate that no further evaluation or treatment is required during the course of study participation (i.e., within approximately 10 months after screening). A prior printed cytology report may be used in place of performing Pap testing at the Screening Visit 1.

6.15 Management of Abnormal Testing During the Study

Clinically significant study-related results should be managed as follows:

- Gonorrhea or Chlamydia: treatment in accordance with current Centers for Disease Control and Prevention (CDC) guidelines. The IUS should not be removed because of a positive test or a diagnosis of cervicitis
- Hemoglobin/hematocrit and ferritin: a value consistent with clinically significant anemia should be evaluated and treated within the local standard of care

6.16 Management of Unevaluable Testing During the Study

An unevaluable test is any test for which the sample or specimen could not produce a result.

- Screening Phase Tests:
 - Visit 2 allows for repeat of unevaluable tests
 - If the samples or specimens from Visit 2 are also unevaluable then repeat at Visit 3 – the results must be available and reviewed for eligibility prior to enrollment
- Treatment Phase Tests (including Treatment Phase Discontinuation/Early Discontinuation)
 - Unevaluable hemoglobin/hematocrit or ferritin should be repeated as soon as possible at an Unscheduled Visit

7. RISK-BENEFIT AND SAFETY ASSESSMENTS

7.1 Risk-Benefit

7.1.1 Menstrual Changes

Women with heavy menstrual bleeding who use a LNG 52 mg IUS generally experience a change in bleeding patterns with a trend toward reduction of MBL (Lethaby et al., 2009). The reduction in MBL with LNG 52 mg IUS is greater than that achieved with combined oral

contraceptives (COC), tranexamic acid, or long-course (≥ 3 weeks/cycle) oral progestins (Bitzer et al., 2015).

In a randomized study comparing LNG 52 mg IUS to MPA over 6 months, approximately 85% of the LNG IUS users had successful treatment compared to 22% of MPA users. Treatment success was defined as achieving MBL of <80 mL and at least a 50% reduction from baseline. Additionally, bleeding was rated as significantly improved according to investigator assessment (93.6% LNG IUS vs. 61.0% MPA) and self-assessment (93.6% LNG IUS vs. 67.1% MPA) (Kaunitz et al., 2010). In a randomized study in Europe comparing LNG20 IUS to Mirena, both products produced similar reductions in MBL after the 6 months of study treatment (79.0% vs. 79.2%, respectively) (Mawet et al., 2014).

A study comparing the LNG 52 mg IUS to a usual-treatment group (tranexamic acid, mefenamic acid, COC or oral progesterone) demonstrated that improvements as measured by the patient-reported Menorrhagia Multi-Attribute Scale (MMAS) were significantly higher at the end of 6 months of treatment with the LNG IUS group compared to the usual treatment group (32.7 points and 21.4 points, respectively). Additionally, improvements in all MMAS domains (practical difficulties, social life, family life, work and daily routine, psychological well-being, and physical health) were significantly better for the LNG IUS group. At the end of two-years 64% of the LNG IUS group continued to use the product compared to 38% of the usual-treatment group (Gupta et al., 2013).

Hemoglobin and ferritin values increase with LNG 52 mg IUS use in women with HMB. In a randomized study assessing the efficacy of a LNG IUS and oral MPA (10 mg/day for 10 days) in women with confirmed HMB, hemoglobin and serum ferritin levels were assessed at baseline, and at Cycles 3 and 6 of treatment. Baseline median hemoglobin and ferritin levels were 12.4 g/dL and 19.0 mcg/L with the LNG IUS and 12.2 g/dL and 19.0 mcg/L with oral MPA, respectively. At Cycle 6, the corresponding medians were 13.4 g/dL and 34.0 mcg/L with the LNG IUS and 12.6 g/dL and 21.0 mcg/L with oral MPA (Kaunitz et al., 2010). The increases from baseline to Cycle 6 were greater in the LNG IUS group than in the oral MPA group for hemoglobin levels (7.5% vs. 1.9%; $p < .001$) and median serum ferritin levels (68.8% vs. 14.3%; $p < .001$).

Of note, amenorrhea rates in women who use the LNG 52 mg IUS for HMB are lower than the rates reported in women who use the LNG 52 mg IUS primarily for contraception. In contracepting women, approximately 20% of women are amenorrheic for a period of 90 days or more by the end of the first year of use (Andersson et al., 1994, Schreiber et al., 2018); this amenorrhea rate is reached within about 9 months of use (Schreiber et al., 2018). Pooled data from four randomized trials comparing the levonorgestrel 52 mg IUS to medroxyprogesterone acetate orally, tranexamic acid orally, mefenamic acid orally and endometrial resection in 163 women with HMB demonstrates the change in bleeding seen in this specific population (Jensen et al., 2013). Amenorrhea rates in this population were 2% at 6 months and 9% at one year. By one year, an additional 24% were reporting infrequent bleeding/spotting. Only 6% of women using the LNG 52 mg IUS for HMB in these trials discontinued for bleeding complaints.

Overall, participants are expected to primarily experience a reduction in flow with study product use.

